15 CLINICAL PHARMACOKINETIC AND PHARMACODYNAMIC ANALYSES

The PK endpoints for this study are as follows:

- Plasma concentration of pimavanserin and AC-279
- Pimavanserin PK parameters using a population PK approach

Pimavanserin and AC-279 plasma concentration data collected in the double-blind period will not be available to the Sponsor until the unblinding of the clinical database at the end of the study.

If data allow, population PK and PK/PD analyses may be performed to further characterize the PK profile and exposure response relationship of pimavanserin and AC-279 using

measures of safety, and efficacy parameters. The results of population PK and PK/PD modeling will be presented in a separate report.

Concentrations that are below the limit of quantitation (LLOQ) will be displayed as “LLOQ” in the data listings and imputed as 0 for computing summary statistics.

15.1 Analysis for the Open-label Pharmacokinetic Analysis Set

Pharmacokinetic samples are collected at Baseline, and Weeks 8 and 12 during the open-label period, and also at any early termination visit or the visit immediately following any SAE or an AE leading to discontinuation in the open-label period.

Plasma concentrations for pimavanserin and AC-279 will be summarized by visit using descriptive statistics for the Open-label Pharmacokinetic Analysis Set.

15.2 Analysis for the Double-blind Pharmacokinetic Analysis Set

In addition to the open-label assessments at Baseline, and Weeks 8 and 12 during the open-label period, pharmacokinetic samples are collected at double-blind Weeks 13, 22, and 38 of the double-blind period, and also at any early termination visit or the visit immediately following any SAE or an AE leading to discontinuation in the double-blind period.

Summaries for the Double-blind Pharmacokinetic Analysis Set will include both the open-label and double-blind study periods.

Plasma concentrations for pimavanserin and AC-279 will be summarized by visit using descriptive statistics for both open-label and double-blind visits.

16 UNBLINDED INTERIM EFFICACY ANALYSIS

The database cutoff date for the interim analysis is defined as the date that the adjudication of the 38th relapse event is complete (complete is defined as when the data has been entered by the responsible reviewer, source data verified by the independent adjudication committee project manager, and entry restricted to further modification). Double-blind discontinuations that occur on or before the database cutoff date will be adjudicated and included in the interim analysis. The ITT Analysis Set for the interim analysis will include all subjects randomized on or before the database cutoff date.

The interim analysis will be based on the interim analysis dataset, created from the interim analysis data extract. Data occurring after the database cutoff date will not be included in the interim analysis dataset; however, data that occurs [e.g., from a visit] on or before the database cutoff date but are entered into the clinical database in the period between the database cutoff date and the date of the interim analysis data extract would be included in the interim analysis datasets. The final database will be locked after all data are included at study termination. If the study is stopped at the interim analysis, sensitivity analyses investigating the impact of overrun events (See [Section 16.2.2](#)) will be based on datasets created from the final database. If the study is not stopped at the interim analysis, the primary analysis of the primary and key secondary efficacy endpoints will be based on the final database using all data collected up until the study discontinuation date.

16.1 Primary Efficacy Endpoint

An interim analysis evaluating efficacy based on the primary efficacy endpoint will be conducted by an independent statistical group (ISG) when at least 38 adjudicated relapse events determined by the IAC have been accrued. The ISG is not affiliated with the Sponsor or the DSMB. The ISG statistician will disseminate the unblinded interim results at the closed session of the DSMB meeting. In order to protect the blinding and the integrity of this study, the actual computational output will be securely stored by the ISG and retained until the study is unblinded after the final database lock.

Table 9 displays the O’Brien-Fleming stopping boundary information for the group sequential design having one interim analysis if it is conducted with exactly 38 relapse events and a final analysis to be conducted with exactly 75 relapse events.

Table 9 O’Brien-Fleming Stopping Boundary Information

			Stopping Boundary: P-value Scale	
Stage	Relapse Events	Proportion	1-sided	2-sided
Interim	38	0.5067	0.0027	0.0054
Final	75	1.0000	0.0239	0.0479

In the event that not exactly 38 relapse events have accrued at the interim analysis, the O’Brien-Fleming stopping boundary will be recalculated based on the actual number of

relapse events accrued at the interim analysis. The decision to stop or continue the study will be made based on this recalculated boundary. More specifically, let Z_1 be the Wald test statistics evaluated at the time of interim analysis and let Z_2 be the Wald test statistics at the time of the final analysis. The test statistics are constructed such that a negative value favors the study drug. Let n be the number of relapse events observed at interim time and N be the total number of events and $t = \frac{n}{N}$ be the information fraction for the interim analysis. At the trial design stage, the plan is to take $n = 38, N = 75$ and $t = \frac{38}{75}$ which implies that the correlation between Z_1 and Z_2 is \sqrt{t} . Let c be a constant such that

$$P\left(Z_1 < \frac{c}{\sqrt{t}}\right) + P\left(Z_1 \geq \frac{c}{\sqrt{t}}, Z_2 < c\right) = 0.025.$$

The one-sided P-value scale boundary for the interim analysis is $p_1^{(1)} = \Phi\left(\frac{c}{\sqrt{t}}\right)$ and the one-sided P-value scale boundary for final analysis is $p_2^{(1)} = \Phi(c)$, where $\Phi(\cdot)$ is the standard normal cumulative distribution function.

At the trial implementation stage, the observed number of relapse events might be different from the planned one. Denote the actual observed number of events at the interim by n^* and let $t^* = \frac{n^*}{75}$ be the observed information fraction at the time of interim analysis.

Let c^* be the constant satisfying the following equation

$$P\left(Z_1 < \frac{c^*}{\sqrt{t^*}}\right) + P\left(Z_1 \geq \frac{c^*}{\sqrt{t^*}}, Z_2 < c^*\right) = 0.025,$$

where the updated correlation between Z_1 and Z_2 is $\sqrt{t^*}$. Then the updated one-sided P-value scale boundaries for the interim and final analyses are given by $p_1^{(1)*} = \Phi\left(\frac{c^*}{\sqrt{t^*}}\right)$ and $p_2^{(1)*} = \Phi(c^*)$.

At the interim analysis, if the observed one-sided p-value from the Cox regression analysis is less than the corresponding lower stopping boundary p-value $p_1^{(1)*}$, then the null hypothesis will be rejected with the conclusion that the study demonstrates superiority of pimavanserin compared to placebo. Conversely, if the observed one-sided p-value is greater than or equal to the lower stopping boundary p-value, the null hypothesis will not be rejected and the study

recruitment will continue until 75 adjudicated relapse events have been accrued for the final analysis. At the final stage, if the observed p-value is less than the corresponding lower stopping boundary p-value $p_2^{(1)*}$, then the null hypothesis will be rejected with the conclusion that the study demonstrates superiority of pimavanserin compared to placebo. In the event that not exactly 75 relapse events have accrued at the final analysis, the O'Brien-Fleming stopping boundary will be recalculated based on the actual number of relapse events accrued at the interim and final analyses and the information fraction. This recalculated boundary will be used to determine superiority of pimavanserin compared to placebo. More specifically, let

$\alpha_1 = \Phi\left(\frac{c^*}{\sqrt{t^*}}\right)$ denote the actual type I error spent at the interim analysis time. Let \tilde{N} be the observed number of relapse events at the final analysis and $\tilde{t} = \frac{n^*}{\tilde{N}}$. The one-sided P-value scale boundary for the final analysis is given by $\Phi(\tilde{c})$ where the \tilde{c} satisfies the following equation

$$\alpha_1 + P\left(Z_1 \geq \frac{c^*}{\sqrt{t^*}}, Z_2 < \tilde{c}\right) = 0.025,$$

and where the correlation between Z_1 and Z_2 is $\sqrt{\tilde{t}}$.

16.2 Key Secondary Efficacy Endpoint

Testing of the key secondary endpoint will be conducted at most once either at the interim analysis or the final analysis provided that the primary endpoint reaches statistical significance. The test statistics are constructed such that a negative value favors the study drug.

An O'Brien-Fleming stopping boundary will also be used for the key secondary endpoint. Let Y_1 and Y_2 be the Wald statistics for testing the key secondary efficacy endpoint at the interim and final analysis. The one-sided P-value scale boundary for the key secondary efficacy endpoint at the interim analysis is given by

$$p_1^{(2)*} = \alpha_1,$$

i.e. the same type I error spent at the interim analysis for the primary efficacy endpoint.

At the time of the final analysis, the one-sided P-value scale boundary is $p_2^{(2)*} = \Phi(d)$ where d satisfies the following equation

$$\alpha_1 + P\left(Y_1 \geq \frac{c^*}{\sqrt{t^*}}, Y_2 < d\right) = 0.025,$$

and where the correlation between Y_1 and Y_2 is given by $\sqrt{\frac{m}{M}}$ and m is the observed number of discontinuation events from the double-blind period at the time of interim analysis and M is the total number of discontinuation events at the final analysis.

16.2.1 Overrunning of Relapse Events at Interim Analysis

If the decision to stop the study for efficacy at the interim analysis is triggered, an overrun in termination events may occur if double-blind termination events occur after the database cutoff date for the interim analysis. For the primary efficacy endpoint defined by adjudicated relapse events, the overrun includes events that occur between the database cutoff date and the study discontinuation date. These events will be adjudicated by the Independent Adjudication Committee and will be included in the sensitivity analysis. Early terminations and relapse events that occur after the study discontinuation date will not be adjudicated and thus will not be included in this sensitivity analysis. Sensitivity analysis of overrun events described in [Section 13.1.2](#) will be considered supportive.

16.2.2 Analysis Following a Sequential Test

To account for the fact that a sequential design is used, the stage-wise ordering of the sample space will be used to compute an adjusted estimate for the hazard ratio, 95% confidence interval, and p-value following rejection of the null hypothesis at the final analysis, if the study was not stopped early at the interim analysis ([Tsiatis, et. al., 1984](#)).

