3.2 Randomization

At Week 12 (Visit 6), subjects who meet response criteria will be randomized in a 1:1 ratio to either continue receiving pimavanserin at the current dose level or to receive matched placebo, using an interactive response technology system. Randomization will be stratified by:

- Most likely dementia subtype or most prominent cause of dementia (defined as designated dementia subtype):
 - Alzheimer’s disease or frontotemporal dementia (FTD) spectrum disorders
 - Vascular dementia
 - Parkinson’s disease dementia or dementia with Lewy bodies
- Region (North America, Western Europe, Eastern Europe, Asia Pacific, Latin America)

The assignments will be based on a pre-generated permuted-block randomization schedule. Blinding will be assured by restricting access of Investigators and Sponsor personnel and/or designee to the treatment codes, and providing identical tablets and packaging for the pimavanserin and placebo treatments.

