3.4 Determination of Sample Size

This study will enroll approximately 356 subjects in order to randomize approximately 178 subjects with dementia-related psychosis who meet response criteria at Weeks 8 and 12 of the open-label period.

The sample size calculation was based on the following assumptions: a placebo relapse event rate of 60% over 26 weeks; a pimavanserin relapse event rate of 35% over 26 weeks (hazard ratio = 0.47); a dropout rate of 25% over 26 weeks; an overall two-sided alpha level of 0.05; use of a one-sided (0.025) O’Brien-Fleming stopping boundary to adjust for a single interim

analysis that will be performed when one half of the total planned number of post-randomization relapse events have occurred; and a power of 90%. The total number of post-randomization relapse events required at the final analysis is 75 and the calculated sample size is 89 in each of the two treatment groups (giving a total estimate of 178 subjects). Study enrollment will be closed when approximately 178 subjects have been randomized in the double-blind period or when 75 adjudicated post-randomization relapse events have occurred. In the event that the randomization rate is lower than anticipated and/or the relapse event rate is lower than anticipated, the number enrolled and randomized may be increased up to a maximum of 400 randomized subjects in order to observe 75 post-randomization relapse events. If fewer than 75 post-randomization relapse events have been observed after 400 randomized subjects have completed the study or terminated early, the study will end. An interim efficacy analysis will be performed, and the study may be terminated early if the interim analysis results meet prespecified stopping criteria.(see [Section 16](#))

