13 METHODS OF EFFICACY ANALYSES

13.1 Primary Efficacy Analysis

The primary efficacy endpoint is the time from randomization to relapse in the double-blind period. The hypotheses are stated in terms of the hazard ratio, $HR = \lambda_{PIM} / \lambda_{PBO}$, where λ_{PIM} and λ_{PBO} denote the hazard rates of relapse for the pimavanserin group (20 mg and 34 mg combined) and the placebo group, respectively.

The null hypothesis for the primary efficacy endpoint is: $HR = 1$

The alternative hypothesis for the primary efficacy endpoint is: $HR \neq 1$

The primary efficacy analysis will be based on adjudicated relapse events determined by the IAC for the ITT Analysis Set. If the study is stopped at the interim analysis, the primary efficacy analysis will be based on the interim analysis dataset (see [Section 16](#) for additional details). If the study is not stopped at the interim analysis, the primary analysis will be based on all data collected up until the study discontinuation date; data collected after the study discontinuation date will not be used in the primary analysis.

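### No bias-reduced hazard ratio is planned for an interim stop, and at the final analysis the sequentially adjusted figures appear only if the test succeeds

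*SAP*

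**What the plan says.** SAP 16.2.2 names stage-wise ordering as the way to allow for the sequential design and limits it to results obtained "following rejection of the null hypothesis at the final analysis, if the study was not stopped early at the interim analysis".

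For an early stop, SAP 13.1 says: "If the study is stopped at the interim analysis, the primary efficacy analysis will be based on the interim analysis dataset". The figures it presents are the HR, standard error, 95% interval and p-value from the Cox model, with no sequential adjustment.

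Two other provisions bear on the point:
- SAP 13.1.2 and 16.2.1 plan a supportive analysis after an early stop that adds the relapses adjudicated up to the study discontinuation date (the overrun). SAP 13.1.2 puts the primary and sensitivity HRs in one forest plot.
- Success is decided by the boundary in SAP 16.1 (Table 9), recalculated for the actual event counts. Protocol 9.5.1 calls the reported Cox p-value nominal.

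**The concern.** A trial that stops at an interim look for efficacy does so because the estimate at that look was extreme. The HR reported after such a stop is therefore too favourable on average, and more so the earlier the look and the weaker the true effect. SAP 16.2.2 exists to allow for the sequential design, yet it is silent on the outcome in which that design most affects the point estimate. An estimator named before unblinding is credible; one chosen after an early stop is much less so.

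At the final analysis, the adjusted interval depends on the test succeeding. If the test narrowly fails, the unadjusted 95% interval stands, and it can exclude 1 when the test did not reject. At stake are the size of the reported effect and its consistency with the test, not the error rate of the test.

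**Working it through.** **Inputs.** Events 38 and 75, and one-sided 0.025 (SAP 16.1); design HR 0.47, which is ln 0.65 / ln 0.40 (SAP 3.4); subjects "randomized in a 1:1 ratio" (SAP 3.2). Assumptions: log HR approximately normal with standard error 2/√events, exactly 38 and 75 events, no covariate effects. True HRs other than 0.47 are illustrative.

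**1. The plan's own boundary.** With t = 38/75 = 0.5067, solving the SAP 16.1 equation gives c = −1.978. One-sided levels are 0.00272 (interim) and 0.02395 (final); two-sided, 0.00545 and 0.04789. Table 9 states 0.0027, 0.0239, 0.0054 and 0.0479, so it is reproduced.

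**2. HR needed to cross.**
- Interim: z boundary a = −1.978/√0.5067 = −2.779; s1 = 2/√38 = 0.3244; exp(−2.779 × 0.3244) = 0.406.
- Final: s2 = 2/√75 = 0.2309; exp(−1.978 × 0.2309) = 0.633.

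**3. Exaggeration given a stop.** With θ the true log HR and u = a − θ/s1, P(stop) = Φ(u) and the mean log HR given a stop is θ − s1·φ(u)/Φ(u). For HR 0.47: θ = −0.755, u = −0.452, Φ(u) = 0.326, φ(u) = 0.360. The mean is −0.755 − 0.3244 × 0.360/0.326 = −1.114, an HR of 0.328. The last column is from simulation (2 million trials).

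| True HR | P(stop at interim) | Geometric mean HR given a stop | Geometric mean HR given rejection at the final |
|---|---|---|---|
| 0.47 | 32.6% | 0.328 | 0.486 |
| 0.60 | 11.4% | 0.347 | 0.532 |
| 0.70 | 4.6% | 0.355 | 0.553 |

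The HR reported after a stop hardly depends on the truth.

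**4. What stage-wise ordering would do at the interim.** At stage 1 the tail probability is simply P(Z1 < z1), as in a fixed design. An observed 0.38 gives 0.380 (0.201 to 0.718) adjusted and unadjusted alike; 0.35 gives 0.350 (0.185 to 0.661) both ways. Lifting the restriction would change no interim number.

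**5. What a bias-adjusted estimate would do.** Averaged over both stages, the expected estimate is θ − s1(1 − t)φ(u). The adjusted estimate is the θ whose expectation equals the observed log HR. For an observed 0.35, try HR 0.372: θ = −0.989, u = 0.269, φ(u) = 0.385. Then −0.989 − 0.3244 × 0.4933 × 0.385 = −1.051, an HR of 0.35, as required. In the same way 0.40 becomes 0.426, 0.38 becomes 0.405 and 0.30 becomes 0.314.

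**6. What the planned overrun analysis would do.** The documents give no overrun count, so k = 5 to 20 further events is assumed. The mean log HR given a stop becomes [38 × (interim mean) + kθ]/(38 + k). At true HR 0.47 and k = 10: (38 × −1.114 + 10 × −0.755)/48 = −1.039, an HR of 0.354. For k = 5, 15 and 20 it is 0.342, 0.363 and 0.372. At true HR 0.60 the range over k = 5 to 20 is 0.369 to 0.419.

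**7. The final analysis.** The planned adjustment is small near the boundary (0.60 becomes 0.602, 0.55 becomes 0.555, 0.50 becomes 0.510) and larger for more extreme results (0.42 becomes 0.449). Test and unadjusted interval disagree when z lies between −1.978 and −1.960, that is, HR about 0.633 to 0.636. At z = −1.97 the unadjusted upper limit is exp[(−1.97 + 1.96) × 0.2309] = 0.998; the stage-wise upper limit is 1.002, with p = 0.051. The chance of reaching the final analysis and landing in that window is 0.3% at true HR 0.47, 0.7% at 0.60 and 0.70, and 0.1% at 1.

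**The case against.** The strongest reply is that nothing is lost by the restriction in SAP 16.2.2. A reader might infer that limiting the adjustment to the final analysis is what leaves the interim HR uncorrected, or that the interval and p-value after an early stop are invalid. Step 4 shows otherwise: stage-wise ordering returns the unadjusted values at stage 1. This part of the objection stands in full. What remains is that no other estimator is named.

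Second, a bias-adjusted estimate does little about the exaggeration given a stop. It moves 0.35 by about 0.02 and 0.40 by about 0.03, against a gap of 0.47 − 0.33 = 0.14 at the design HR. That also stands, and the report should say so.

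Third, the overrun analysis already attenuates the HR, and with about 10 or more extra events by at least as much, in a display beside the primary result. This is a fair point, but the overrun count is unknown in advance, and the analysis refits the same Cox model without any sequential correction.

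Fourth, the p-value window is rare, success is judged by the boundary, and the p-value is labelled nominal. The plan also reports other 95% intervals, from the imputation and sensitivity analyses, though none is sequentially adjusted. All true; it limits the weight of the second gap without removing it.

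**Conclusion.** The point holds as two minor gaps in reporting.

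- **Interim stop.** The inference is valid, but no bias-reduced HR is planned and stage-wise ordering cannot supply one. The conditional exaggeration is large (mean 0.33 for a true 0.47). The one-in-three chance of meeting it applies only at the design HR; it falls to 11% and 5% at true HRs of 0.60 and 0.70, where the exaggeration is greater.
- **Final analysis.** Making the adjusted figures conditional on rejection allows the test and the only planned primary interval to disagree, with probability 0.1% to 0.7%.

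The documents do not support a claim of inflated type I error, nor any statement about what use will be made of the HR. The figures rest on the normal approximation and on exactly 38 and 75 events. The overrun range is an assumption.

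**What to change.** 1. **If the trial stops at the interim**, pre-specify in SAP 16.2.2 a supplementary bias-adjusted maximum likelihood estimate of the HR. Show it beside the unadjusted primary HR and the already planned overrun-inclusive HR. State that it corrects unconditional bias only and does not remove the full exaggeration given a stop. Estimation conditional on stopping is not a practical substitute, because it is unstable near the boundary: an observed 0.38 becomes 1.77.
2. **At the final analysis**, delete the condition that the null hypothesis be rejected, and report the stage-wise adjusted HR, interval and p-value whatever the result.

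The cost is a few lines of SAP text and one extra calculation. The downside is a slightly less favourable HR shown beside the primary one. Boundaries, event counts and the primary test stay as they are.

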17 DATA AND SAFETY MONITORING BOARD

An independent Data and Safety Monitoring Board (DSMB) will review interim safety data including data on AEs and SAEs. The DSMB will be independent of the Sponsor and the Investigators and will be empowered to recommend stopping the study due to safety concerns. In addition, the DSMB will review the results of the pre-planned unblinded interim

analyses conducted by the ISG. The roles and responsibilities of DSMB members and ISG and planned frequency of meetings are detailed in the DSMB Charter.

The ISG will produce unblinded interim statistical outputs and provide these outputs to DSMB members using a secure method. The Sponsor and the Investigators will remain blinded until the official unblinding of the database at the end of the study. The outputs presented to DSMB members by the independent statistician will be consistent with what is described in the DSMB Charter.

